**Background:**

Neuromuscular blocking drugs are used frequently during general anesthesia. The effects of neuromuscular blocking drugs are measured using a twitch monitor, that stimulates the ulnar nerve and measures the evoked response of the adductor pollicis muscle (thumb flexion), or other intrinsic hand muscle. When a series of 4 twitches is administered, the ratio of the first to the fourth twitch (train-of-four ratio) may be used to gauge the degree of muscle relaxation. A train-of-four ratio of 0.9 or greater is considered to represent adequate recovery from neuromuscular blockade. At the end of surgery, antagonists of neuromuscular blockade are commonly administered to reverse any remaining muscle relaxation. Sugammadex is a highly effective reversal agent of the aminosteroid neuromuscular blocking drugs rocuronium and vecuronium, which are the most commonly used neuromuscular blocking drugs. The dose-response relationship for sugammadex has never been completely determined. The dose of sugammadex depends upon the degree of neuromuscular blockade. When at least 1 twitch of the train-of-four is present, the recommended dose of sugammadex is 2 mg/kg. When there are no twitches of the train-of-four present, but at least 1 count of the post tetanic count is present, the recommended dose of sugammadex is 4 mg/kg. However, in several dose ranging studies of sugammadex, and in using sugammadex clinically, we and others have determined that smaller doses of sugammadex, often much less than 2 mg/kg, may be effective producing a train-of-four ratio of 0.9 or greater. Sugammadex binds (encapsulates) aminosteroid neuromuscular blocking drugs tightly and the sugammadex-aminosteroid complex is subsequently cleared by the kidney. Therefore we do not expect that recurrence of neuromuscular blockade would occur, even after small doses of sugammadex, as long as the dose of sugammadex is adequate to produce a train-of-four ratio of 0.9. Additional studies are needed to determine the dose-response for sugammadex and to confirm that recurrence of neuromuscular blockade does not occur after small doses of sugammadex. The purpose of the proposed study is to test the hypothesis that when sugammadex is titrated in 50 mg increments until the train-of-four ratio is 0.9 or greater, that this train-of-four ratio is maintained and there is no recurrence of neuromuscular blockade.

**Objectives:**

The hypothesis is that when sugammadex is titrated in 50 mg increments until a train-of-four ratio of at least 0.9 is reached, that the train-four-ratio will remain at least 0.9 for 6 hours or until extubation, whichever comes first.

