#### Statistical analysis:

Sample size is based on previous sugammadex dose-finding studies. The sample size in this study is similar to the largest previous sugammadex dose-finding studies. Descriptive statistics will be presented as number (%) for categorical variables or mean  $\pm$  standard deviation (SD) for continuous variables. Outcome variables (sugammadex dose) will be compared among twitch response groups using two-sample Student's *t* test with the assumption of unequal variance (Satterthwaite's degrees of freedom), ANOVA, two-sample test of proportions, Wilcoxon rank sum test and Pearson's Chi-squared test as appropriate. All P values will be 2-sided, and statistical significance will be defined as a P value of  $< 0.05$ . All statistical analyses will be performed with STATA 11.0 (Stata Corp LP, College Station, TX). Patient and procedure characteristics will be analyzed with R 4.2.1s (R Foundation for Statistical Computing, Vienna, Austria).

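### The hypothesis is an absolute no-recurrence claim, but the plan gives no upper bound for recurrence and no recurrence-based sample size

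*Combined protocol and SAP*

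**What the plan says.** The Objectives section holds the trial's only hypothesis: once titration has brought the ratio to 0.9, "that the train-four-ratio will remain at least 0.9 for 6 hours or until extubation, whichever comes first". The Background gives the same hypothesis in other words, "that this train-of-four ratio is maintained and there is no recurrence of neuromuscular blockade", and says that further studies are needed "to confirm that recurrence of neuromuscular blockade does not occur after small doses of sugammadex".

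The Statistical analysis section deals with size in two sentences: "Sample size is based on previous sugammadex dose-finding studies" and "The sample size in this study is similar to the largest previous sugammadex dose-finding studies". It gives no calculation, expected recurrence rate or precision target. The one outcome it names is dose: "Outcome variables (sugammadex dose) will be compared among twitch response groups". The only planned summary that could cover recurrence is generic, "Descriptive statistics will be presented as number (%) for categorical variables", with no interval. Significance is set at a two-sided 0.05 but is not attached to any analysis of recurrence.

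Elsewhere the plan treats recurrence as possible. Study procedures provides for more sugammadex if a ratio falls below 0.9, Anticipated risks allows a small hypothetical chance of recurrence, and Data and safety monitoring defines an adverse event by the need for sugammadex after the operating room.

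**The concern.** The cut-off of 0.9 classifies a reading in one patient. Nothing says what proportion of patients may fall below it, or how precisely that proportion must be known, for the hypothesis to count as supported. Taken literally, the wording sets the tolerable proportion at 0%, which data can contradict but never establish.

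What is at stake is what the trial may conclude. If no patient has a ratio below 0.9, the plan as written allows a report of 0% with no interval, beside a hypothesis of no recurrence. A reader could take that as confirmation without seeing which rates the data leave open. If one or two patients do fall below 0.9, nothing fixed in advance says whether this counts against the hypothesis, and the interpretation would be chosen after the data are seen.

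**Working it through.** **Inputs.** From the documents: the absolute hypothesis (Objectives, Background) and the two-sided 0.05 level (Statistical analysis), which corresponds to a 95% interval. Neither a number of patients nor a numerical recurrence rate appears in the available text, so there is no planned figure to reproduce. The values of n and of the true rate below are assumptions.

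**Upper limit with 0 events.** The exact (Clopper-Pearson) two-sided 95% upper limit solves (1−p)^n = 0.025, so U = 1 − 0.025^(1/n). For n=20: ln 0.025 = −3.689; divided by 20 this is −0.1844; exp(−0.1844) = 0.832; U = 16.8%.

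**Upper limit with 1 event.** It solves (1−p)^n + n·p·(1−p)^(n−1) = 0.025.

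**Chance of 0 events at true rate p:** (1−p)^n. **Chance of at least 1 event:** 1 − (1−p)^n.

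| Assumed n | Upper limit, 0 events | Upper limit, 1 event | Chance of 0 events, true rate 2% | Chance of ≥1 event, true rate 0.5% |
|---|---|---|---|---|
| 20 | 16.8% | 24.9% | 67% | 9.5% |
| 50 | 7.1% | 10.7% | 36% | 22% |
| 100 | 3.6% | 5.5% | 13% | 39% |
| 200 | 1.8% | 2.8% | 1.8% | 63% |

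The first two result columns show what the trial could exclude. The last two show what follows if the absolute wording is taken literally: at a given non-zero true rate, a smaller trial is more likely to see no event and a larger one is more likely to see at least one.

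**Patients needed to exclude a given rate.** With 0 events the smallest n is ln(0.025)/ln(1−p0), rounded up. With 1 event it is the smallest n at which the chance of 0 or 1 events at p0 is no more than 0.025. The rates are illustrations only.

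| Rate to exclude (p0) | n, 0 events | n, 1 event |
|---|---|---|
| 10% | 36 | 54 |
| 5% | 72 | 110 |
| 2% | 183 | 277 |

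**The case against.** The strongest reply is that this is a single-arm, largely descriptive study whose hypothesis is in ordinary scientific wording. Recurrence is measured on arrival in intensive care and hourly after that, counts and percentages are planned, and any reader could compute an interval from them. A study of this kind can be sound through estimation alone, so a formal pass mark is debatable. The link to dose-finding work also has a basis in the text, since the Background names the dose-response relationship as a need and dose is the named outcome. Much of this stands, and it is why a pass mark is treated below as optional. It does not remove the gap: the Background speaks of testing a hypothesis and of confirmation, and even a purely descriptive aim needs an interval and a statement of precision, which the plan lacks.

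Three stronger readings are tempting and not supported:

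- A reader might infer that the plan treats zero events as confirmation and one event as refutation. That follows from the absolute wording, but it is not a written rule. The last two columns of the first table are therefore not operating characteristics of the plan.
- A reader might infer that the earlier dose-finding studies were sized for a purpose unsuited to recurrence. The documents do not say how those studies were sized.
- A reader might infer that the trial is too small. No number of patients appears in the available text and some pages were removed from it, so no error in a planned number can be alleged.

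**Conclusion.** The point holds as a gap between the claim and what the plan can support. The hypothesis is absolute, and nothing in the Statistical analysis section bounds recurrence, says what rate would be tolerable, or ties the sample size to recurrence. Zero events could therefore be reported as absence of recurrence when the upper limit is anywhere from 16.8% (n=20) to 1.8% (n=200).

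The practical size depends on an n that is not visible: considerable at the low end of the range, modest at the high end. The figures treat patients as independent, with one yes/no outcome each. The gap itself does not depend on n.

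It would go too far to say that the plan cannot address its hypothesis at all. The necessary readings are taken. What is missing is the interval, the wording of the conclusion and a statement of what the planned n can exclude.

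**What to change.** **Objectives** (with the purpose sentence in the Background brought into line): restate the aim as estimating, and bounding from above, the proportion of patients with any train-of-four ratio below 0.9 after reversal, up to 6 hours or extubation if sooner.

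**Statistical analysis:**

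- Report that proportion with an exact (Clopper-Pearson) 95% confidence interval.
- Word the conclusion as a recurrence rate no higher than the upper limit, not as no recurrence.
- State the planned n and the upper limit it gives with 0 and with 1 event, beside the comparison with earlier studies.

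**Only if a confirmatory claim is wanted:** fix a maximum acceptable rate in advance on clinical grounds and require the upper limit to fall below it. The rate should not be derived from n, because a smaller trial would then simply earn a looser standard. A rate lying between the 0-event and 1-event limits (3.6% to 5.5% at n=100) still lets a single event decide the result, so the largest passing event count should be stated. If the planned n cannot meet the chosen rate, present the result as estimation only.

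**Cost:** the estimation route changes wording and adds one interval; it needs no further readings or patients. Its downside is a less absolute headline claim. The confirmatory route may need more patients than planned, depending on the rate chosen, as the second table shows.

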**Study design:**

Cardiac surgery patients will receive sugammadex in 50 mg increments at the end of surgery, until the train-of-four ratio is at least 0.9 and the train-of-four ratio will be measured hourly in the ICU for 6 hours or until extubation, whichever comes first.

**Participants:**

Cardiac surgery patients >18 years of age who will routinely remain intubated following surgery with planned admission to the intensive care unit

**Inclusion criteria:**

Cardiac surgery patients >18 years of age who will routinely remain intubated following surgery with planned admission to the intensive care unit

**Exclusion criteria:**

Allergy or other contraindication to the use of sugammadex

#### Recruiting and screening:

An investigator or research assistant will review the electronic procedure schedule and identify potential subjects. Either a research assistant or investigator will approach potential subjects to obtain written consent on the day of the procedure in the pre-operative area prior to any sedation. Alternatively, patients may be contacted by phone to assess their potential interest in participation, with completion of the written consent process in the pre-operative area on the day of surgery, prior to any sedation.

#### Study procedures:

1. Standard clinical procedure for monitoring and reversal of neuromuscular blockade—Neuromuscular blockade is monitored with EMG-based quantitative twitch monitoring (TwitchView). At the end of surgery, sugammadex is administered to reverse neuromuscular blockade, as defined by a train-of-four ratio of 0.9 or greater. The patient is transported asleep, intubated and ventilated to the intensive care unit where the train-of-four ratio of 0.9 or greater is confirmed on arrival by the respiratory therapist.
2. Study procedure—Instead of administering a standard dose of sugammadex 2 mg/kg or 4 mg/kg, sugammadex will be titrated in 50 mg increments every 5 minutes until a train-of-four ratio of 0.9 or greater is reached. Train-of-four ratio will be measured on arrival in the intensive care unit and then hourly for 6 hours or until extubation if extubation occurs in <6 hours. If the train-of-four ratio is less than 0.9 at any time, additional sugammadex will be administered until the train-of-four ratio is 0.9 or greater. The twitch monitoring results in the operating room just prior to reversal, following reversal and hourly in the intensive care unit will be recorded, along with sugammadex doses. The total dose of rocuronium or vecuronium and the time period of neuromuscular blocking drug will also be recorded. Data will either be recorded in real time by study assistants or retrieved from the electronic medical record. The patient's age, gender, and weight will be recorded. Data will be obtained by study assistants or from the electronic medical record.

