#### Anticipated risks:

The risks that are specific to this research are minimal (excluding the risk of anesthesia and cardiac surgery, which are not specific to this research). Patients will receive sugammadex regardless of their participation in this study. By participating in this study, patients may receive a smaller dose of sugammadex than they would otherwise receive. Hypothetically, there may be a small chance that a smaller dose of sugammadex could result in a recurrence of neuromuscular blockade. This is mitigated by the fact that the patients will be intubated and ventilated postoperatively, which is routine care following cardiac surgery, thus any recurrence of neuromuscular blockade would not be harmful. If there is any recurrence of neuromuscular blockade, this will be detected by twitch monitoring and additional sugammadex will be administered. The patients participating in this study will not be under anesthesia in the operating room or intensive care unit for a longer time than patients not participating in this study.

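### The only hypothesis concerns recurrence of blockade up to extubation or 6 hours, but the analysis section names only sugammadex dose and plans no recurrence estimate or interval; a smaller gap is that no reading is required near an early extubation

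*Combined protocol and SAP*

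**What the plan says.** **The question.** The Background gives the purpose as testing, for sugammadex titrated in 50 mg steps, "that this train-of-four ratio is maintained and there is no recurrence of neuromuscular blockade". The Objectives section puts a time limit on this: "the train-four-ratio will remain at least 0.9 for 6 hours or until extubation, whichever comes first". No other hypothesis is stated.

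**The readings.** Under Study design, "the train-of-four ratio will be measured hourly in the ICU for 6 hours or until extubation, whichever comes first". Study procedures adds a reading on arrival: the ratio is "measured on arrival in the intensive care unit and then hourly for 6 hours or until extubation". Neither section ties a reading to the moment of extubation. The list under Data variables does not name extubation time, although data may be taken from the medical record. Anticipated risks states: "If there is any recurrence of neuromuscular blockade, this will be detected by twitch monitoring".

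**The analysis.** Under Statistical analysis, "Outcome variables (sugammadex dose) will be compared among twitch response groups", followed by a list of tests. The same section says in general terms: "Descriptive statistics will be presented as number (%) for categorical variables". Recurrence is not mentioned there.

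**Safety reporting.** Data and safety monitoring defines an adverse event as one that requires sugammadex between leaving the operating room and extubation. Study procedures calls for further sugammadex "If the train-of-four ratio is less than 0.9 at any time". A detected recurrence that is treated before extubation is therefore a reportable event.

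**The concern.** The hypothesis and the analysis concern different quantities. The hypothesis is about whether the ratio stays up over time. The analysis is about how much drug was given, compared among groups defined by twitch response. None of those comparisons says how often the ratio fell below 0.9 or how precisely that is known. Followed as written, the plan could report zero recurrences, and a reader could take that as zero risk when the data still allow several per cent.

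The lesser concern is measurement. In a patient who stays intubated, a fall that persists is seen at the next hourly reading. In a patient extubated between readings there is no next reading, so the last part of the hypothesis window goes unobserved. The statement that any recurrence will be detected is not secured by the schedule in that interval.

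**Working it through.** The plan gives no sample size, recurrence risk, power or precision target, so there is no figure of its own to reproduce. Every input below other than the 6-hour limit and the hourly schedule is an assumption.

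**1. What zero or one recurrence would show.** The exact (Clopper-Pearson) two-sided 95% upper limit for 0/n is 1 − 0.025^(1/n).

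| Result | Exact 95% interval |
|---|---|
| 0/50 | 0 to 7.1% |
| 1/50 | 0.05 to 10.65% |
| 0/100 | 0 to 3.6% |
| 1/100 | 0.03 to 5.45% |

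For example, 1 − 0.025^(1/50) = 0.0711.

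**2. Length of the unread interval.** With readings exactly on the hour, extubation at T hours (T below 6) leaves T − floor(T) unread. Extubation at 1 h 59 min leaves 59 minutes. A patient extubated within the first hour has only the arrival reading.

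**3. Risk that falls in the unread interval.** Assumptions:
- a share f of patients is extubated uniformly over 1 to 6 h, and the rest are followed to 6 h;
- a ratio that has fallen stays low until the next reading;
- extubation time is independent of recurrence;
- cumulative risk is F(t) = 1 − exp(−H6·(t/6)^k), with H6 = −ln(1 − p6), where p6 is the 6-hour risk and k = 1 means constant hazard.

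Endpoint risk = (1 − f)·p6 + f·E[F(T)]. Risk captured by readings = (1 − f)·p6 + f·E[F(floor T)]. Unread risk d = f·(E[F(T)] − E[F(floor T)]).

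With p6 = 10% and k = 1: H6 = 0.10536, E[F(T)] = 0.05931 and E[F(floor T)] = 0.05102, a difference of 0.00828 before rounding. Multiplying by f:

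| f | Endpoint risk | Captured | Unread (percentage points) | Share of endpoint risk |
|---|---|---|---|---|
| 25% | 8.98% | 8.78% | 0.21 | 2.3% |
| 50% | 7.97% | 7.55% | 0.41 | 5.2% |
| 75% | 6.95% | 6.33% | 0.62 | 8.9% |

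With p6 = 1% and k = 1, the unread risk is 0.02, 0.04 and 0.06 points.

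Sensitivity to timing, at p6 = 10%: mostly early recurrence (k = 0.5) gives 0.15 to 0.45 points; mostly late recurrence (k = 2) gives 0.23 to 0.70 points.

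**4. Chance that at least one recurrence is unread in an assumed 100 patients**, 1 − (1 − d)^100: 19%, 34% and 46% at a 10% risk for the three values of f, and 2%, 4% and 6% at a 1% risk.

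**The case against.** **Recurrences are already captured.** A recurrence that is detected and treated before extubation is an adverse event under Data and safety monitoring, sugammadex doses and times are recorded, and the general promise of counts and percentages could cover a recurrence count. This stands as far as it goes: the events would not be lost. But neither section names a proportion, a denominator or an interval, and the safety count depends on a reading having been taken.

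**The schedule gap is close to immaterial.** Any hourly schedule leaves time between readings. The Background says recurrence is not expected, and Anticipated risks calls the chance small and hypothetical, so the 1% case is nearer the plan's own premise than the 10% case. The independence assumption may also overstate the gap: if a patient with returning weakness is less likely to be extubated, that patient stays under hourly reading. The documents do not settle this. The objection is largely right, which is why this part is secondary.

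**Measuring until extubation might imply a final reading.** It could be read that way, but none is specified.

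**An added reading is not a pure measurement.** This stands. A value below 0.9 would meet the existing text in Study procedures on further sugammadex. The documents also do not say whether the monitor stays attached between readings.

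**A stronger inference to avoid.** A reader might infer that the trial cannot detect recurrence, or that a substantial share would be missed before extubation. The documents do not support this. Readings on arrival and hourly cover most of the window, and the unread risk is a fraction of a percentage point in nearly all the scenarios above, reaching at most 0.70 points.

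**Conclusion.** The main point holds. The one stated hypothesis has no planned estimate and no statement of precision, because the analysis section names only dose. The consequence is interpretive: zero events would be compatible with a true proportion of up to 7.1% in an assumed 50 patients or 3.6% in an assumed 100, and nothing in the plan makes the report say so. Safety reporting and the general descriptive sentence soften this but do not supply the estimate.

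The secondary point also holds and is small: about 0.02 to 0.06 percentage points at an assumed 1% six-hour risk and 0.2 to 0.6 at 10%. This rests on constant hazard, 25 to 75% of patients extubated uniformly over 1 to 6 h, persistence of a low ratio to the next reading, and extubation time independent of recurrence. On its own it would merit a stated limitation. Together the two points should be addressed, with the analysis section first.

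**What to change.** 1. **Statistical analysis.** Name as the main outcome the proportion of patients with any train-of-four ratio below 0.9 from ICU arrival up to extubation or 6 h, with an exact 95% interval. Each patient counts once, so readings after further sugammadex do not change the classification. Show how many patients were read at arrival and at each of hours 1 to 6. Word the conclusion as applying until extubation or 6 h, and quote the upper limit beside it.

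2. **Data variables.** Add extubation time. ICU arrival time, the time of each reading and the reason for any reading not taken are useful supporting items; most may be retrievable from the medical record.

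3. **Study procedures.** Either record one reading shortly before an extubation that occurs before hour 6, with the monitor already in use, and include it in the table of patients read, or state the unread interval as a limitation. If the reading is added, the sponsor must reconcile it with the existing text on a ratio below 0.9 at any time. No clinical rule is proposed here.

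Cost: one extra table, a few recorded times and at most one short reading per early-extubated patient. Items 1 and 2 can be adopted without the extra reading.
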